10.2. Populations for Analyses

There are 2 analysis populations defined in the protocol:

- Full Analysis Set (FAS): all patients randomized in Stage 2 who received at least 1 dose of trial medication (placebo or setmelanotide) in Stage 2 and have baseline data. Analyses performed on the FAS will be based on patients as randomized.
- Safety Analysis Set: All patients who received at least 1 dose of trial medication.

10.3. Statistical Analyses

A separate SAP will be developed, which will include a more technical and detailed description of the statistical analyses described in this section.

The primary efficacy endpoint of the trial is the proportion of patients by genotype who demonstrate a significant clinically meaningful response (defined below) to setmelanotide at the end of Stage 1:

- For all patients: $\geq 5\%$ reduction in BMI from Baseline

The 95% exact confidence interval will be provided for the primary efficacy endpoint. The analyses of the efficacy endpoints in Stage 1 will be performed based on the safety analysis set, and the analyses of the efficacy endpoints in Stage 2 will be performed based on the FAS, which is defined as all patients randomized in Stage 2 who received at least 1 dose of trial medication (placebo or setmelanotide) in Stage 2 and have baseline data.

AEs/SAEs will be summarized with frequencies and percentages. A by-patient AE data listing including onset and resolution dates, verbatim term, preferred term, treatment, severity, relationship to treatment, action taken, and outcome will be provided.

Safety data including laboratory evaluations and vital signs assessments will be summarized by time of collection. In addition, change from baseline to any post-dose values will be summarized for vital signs and clinical laboratory results. Frequency of patients with abnormal safety laboratory results will be tabulated.

All safety analyses and summary tables will be based on the safety analysis set.

10.3.1. Interim Analyses

There are no planned interim analyses.

12. APPENDICES

APPENDIX 1. LIST OF GENES ELIGIBLE FOR ENROLLMENT AND GENETIC TESTING REQUIREMENTS

Patients with genetic variants in the following genes that have been categorized by a Clinical Laboratory Improvement Amendment (CLIA)/College of American Pathologists (CAP)/ISO15189 certified laboratory using American College of Medical Genetics (ACMG) criteria as (1) pathogenic, (2) likely pathogenic, or (3) a variant of uncertain significance as potentially causing dysfunction in the melanocortin-4 receptor pathway and leading to obesity are eligible for this trial:

LEP
ISL1
DNMT3A
TRPC5
PLXNA4
NRP1
SEMA3E
SEMA3F
MECP2
SEMA3A
SEMA3C
PHIP
NRP2
MRAP2
MC3R
CPE
SEMA3B
SEMA3D
SIM1
HTR2C
SEMA3G
KSR2
MAGEL2
RPGRIP1L
TBX3
PLXNA1
CREBBP
PLXNA3
PLXNA2
TUB

GENETIC TESTING REQUIRMENTS:

Eligibility per Inclusion Criterion #1 and assignment to the appropriate sub-study cohort will be based on either:

- a. genetic diagnosis made by a CLIA/CAP/ISO15189 laboratory, or
- b. genetic report available at screening from a non-CLIA/CAP/ISO15189 laboratory, sent for review and adjudication via Variant Interpretation Service (VIS) conducted by PreventionGenetics (PG), a CLIA/CAP/ISO15189 certified laboratory.

In addition to the eligibility testing described above, all patients will have confirmatory diagnosis made based on the PG Uncovering Rare Obesity (URO) 3.0 panel (79 genes +1 chromosomal region).

All randomized patients will be included in the safety and Full Analysis Set (FAS) analyses. The Per-Protocol (PP) analysis will only include patients whose confirmatory diagnosis testing matches the respective sub-study cohort assignment. There are 3 potential scenarios for sub-study cohort assignment:

- If at Screening the genetic diagnosis is derived from PG, a CLIA/CAP/ISO15189 certified laboratory (URO 3.0 panel), the patient will be assigned to the cohort reported in the PG URO 3.0 genetic report. A genetic sample will be taken for confirmatory testing, unless waived by the Sponsor.
- If the genetic diagnosis is derived from a non-CLIA/CAP/ISO15189 laboratory (such as a research academic center laboratory), the genetic report will be reviewed and adjudicated by PG for VIS before the patient enters Screening. The VIS result will be utilized for cohort assignment. A genetic sample will be taken either at the time of screening or at Study Visit 1 (V1) and confirmatory testing will be run using the PG laboratory. If the confirmatory genetic report does not confirm the initial genetic diagnosis and sub-study cohort assignment, then patients will be included in the safety and FAS analyses only, and not in the PP analysis.
- If the genetic diagnosis is derived from a CLIA/CAP/ISO15189 laboratory, other than PG, no PG VIS review is required. A genetic sample will be taken either at the time of screening or at V1 and confirmatory testing will be run using the PG laboratory.

All patients will have genetic samples processed for confirmatory genetic testing. Where permitted by law, all patients may provide additional informed consent to have genetic samples stored for future research purposes.

APPENDIX 2. CONSIDERATIONS FOR REDUCING PAIN AND DISTRESS IN THE PEDIATRIC POPULATION

Although the trial procedures and assessments required per protocol are classified as “No or Minimal Risk” according to the 2008 Guidance Document “Ethical Considerations for Clinical Trials on Medicinal Products Conducted with the Paediatric Population”, considerations for reducing pain and distress in participants <18 years of age are suggested below.

- The clinical trial may only be conducted if it exposes the person concerned to as little burden and other foreseeable risks as possible.
- Physical and emotional pain should be prevented as much as possible, and effectively treated when unavoidable.
- In order to minimize pain, distress, and fear, facilities should be appropriate to childcare, and the personnel should be trained to look after children and supervised by experienced health care professionals. Staff should be trained to communicate with both parents (or legal representative) and children. Generally, this would assume non-adult patients are being studied at experienced pediatric centers.
- For most procedures, the child should always be accompanied by a trial-related staff member who could provide reassurance. At the sign of distress and/or dissent, the procedure should be stopped. A short pause to allow the child to feel in control, further explanation, and an assessment of the situation may be needed to reassure the child, or to decide to definitely abandon the procedure at the discretion of the Investigator.
- In all situations, investigations/interventions should be limited to the minimum required for obtaining valid data and performed using size-/age-appropriate material and devices, including limiting in advance the number of attempts for sampling.
- Trial medication injections should only be performed by caregiver (or home health care professionals), unless the child is of suitable age and competency, and desires the ability to do so.
- Although almost all trial procedures are classified as low risk, risk should be continuously monitored and assessed by appropriate personnel.
- For assessments in which there is a psychological component, measures should be taken to minimize distress. For example, Tanner Staging assessments could utilize a diagram for the child to point to and indicate what stage they currently are, vs. having to have an examination without clothes.

A comment on benefit risk: Risk is very low, from procedures and/or known safety profile of the drug (both clinically and toxicologically, where large margins and preliminary data from juvenile toxicology studies have not identified any new or concerning safety concerns) and based on representative examples of rare genetic diseases of obesity impacting the MC4R pathway, there is the possibility of major benefit.

APPENDIX 3. FITZPATRICK SCALE

Skin Type	Skin Color	Characteristics
I	White; very fair; red or blond hair; blue eyes; freckles	Always burns, never tans
II	White; fair; red or blond hair; blue, hazel, or green eyes	Usually burns, tans with difficulty
III	Cream white; fair with any eye or hair color; very common	Sometimes mild burn, gradually tans
IV	Brown; typical Mediterranean Caucasian skin	Rarely burns, tans with ease
V	Dark Brown; mid-eastern skin types	Very rarely burns, tans very easily
VI	Black	Never burns, tans very easily

[Fitzpatrick TB. Soleil et peau. J Med Esthet. 1975;2:33034.](#)

APPENDIX 4. INJECTION SITE EVALUATIONS

Injection sites will be assessed at the time points outlined in the Schedule of Assessments (Table 1 and Table 2), and in the setting of any injection site reaction adverse experience. This assessment will consider severity and measurement (length and width if applicable) of any instance of erythema, edema, induration, itching, pain/tenderness or other relevant findings.

Local Skin Tolerability Assessment

Reaction	NONE	Mild	Moderate	Severe	Measurement (if applicable)
Erythema* ¹					
Edema*					
Induration* ¹					
Itching					
Pain or Tenderness					
Other: _____					

* If present, region will be measured, length and width as appropriate.

¹ In the event of severe erythema, defined as ≥ 10 cm, and/or induration of the injection area of the size of ≥ 10 cm and in the presence of fever defined as $\geq 38^{\circ}\text{C}$, or based on the Investigator's clinical judgement, the Investigator should contact the Sponsor and discuss therapeutic management of the patient and potential temporary drug discontinuation.

Initials: _____

APPENDIX 5. ADVERSE EVENTS: DEFINITIONS AND PROCEDURES FOR RECORDING, EVALUATING, FOLLOW-UP, AND REPORTING

Definition of Adverse Event (AE)

AE Definition

• An AE is any untoward medical occurrence in a patient or clinical trial patient, temporally associated with the use of trial treatment, whether or not considered related to the trial treatment.• NOTE: An AE can therefore be any unfavorable and unintended sign (including an abnormal laboratory finding), symptom, or disease (new or exacerbated) temporally associated with the use of trial treatment.

Events Meeting the AE Definition

• Any abnormal laboratory test results (hematology, clinical chemistry, or urinalysis) or other safety assessments (e.g., ECG, radiological scans, vital signs measurements), including those that worsen from baseline, considered clinically significant in the medical and scientific judgment of the Investigator (i.e., not related to progression of underlying disease).• Exacerbation of a chronic or intermittent pre-existing condition including either an increase in frequency and/or intensity of the condition.• New conditions detected or diagnosed after trial treatment administration even though it may have been present before the start of the trial.• Signs, symptoms, or the clinical sequelae of a suspected drug-drug interaction.• Signs, symptoms, or the clinical sequelae of a suspected overdose of either trial treatment or a concomitant medication. Overdose per se will not be reported as an AE/SAE unless it is an intentional overdose taken with possible suicidal/self-harming intent. Such overdoses should be reported regardless of sequelae.• “Lack of efficacy” or “failure of expected pharmacological action” per se will not be reported as an AE or SAE. Such instances will be captured in the efficacy assessments. However, the signs, symptoms, and/or clinical sequelae resulting from lack of efficacy will be reported as AE or SAE if they fulfil the definition of an AE or SAE.

Events NOT Meeting the AE Definition

- Any clinically significant abnormal laboratory findings or other abnormal safety assessments which are associated with the underlying disease, unless judged by the Investigator to be more severe than expected for the patient’s condition.
- The disease/disorder being studied or expected progression, signs, or symptoms of the disease/disorder being studied, unless more severe than expected for the patient’s condition.
- Medical or surgical procedure (e.g., endoscopy, appendectomy): the condition that leads to the procedure is the AE.
- Situations in which an untoward medical occurrence did not occur (social and/or convenience admission to a hospital).
- Anticipated day-to-day fluctuations of pre-existing disease(s) or condition(s) present or detected at the start of the trial that do not worsen.

Definition of Serious Adverse Event (SAE)

If an event is not an AE per definition above, then it cannot be an SAE even if serious conditions are met (e.g., hospitalization for signs/symptoms of the disease under study, death due to progression of disease).

A SAE is defined as any untoward medical occurrence that, at any dose:

a. Results in death

b. Is life-threatening

The term ‘life-threatening’ in the definition of ‘serious’ refers to an event in which the patient was at risk of death at the time of the event. It does not refer to an event, which hypothetically might have caused death, if it were more severe.

c. Requires inpatient hospitalization or prolongation of existing hospitalization

In general, hospitalization signifies that the patient has been detained (usually involving at least an overnight stay) at the hospital or emergency ward for observation and/or treatment that would not have been appropriate in the physician’s office or outpatient setting. Complications that occur during hospitalization are AEs. If a complication prolongs hospitalization or fulfills any other serious criteria, the event is serious. When in doubt as to whether “hospitalization” occurred or was necessary, the AE should be considered serious.

Hospitalization for elective treatment of a pre-existing condition that did not worsen from baseline is not considered an AE.

d. Results in persistent disability/incapacity

- The term disability means a substantial disruption of a person’s ability to conduct normal life functions.
- This definition is not intended to include experiences of relatively minor medical significance such as uncomplicated headache, nausea, vomiting, diarrhea, influenza, and accidental trauma (e.g., sprained ankle) which may interfere with or prevent everyday life functions but do not constitute a substantial disruption.

e. Is a congenital anomaly/birth defect

A SAE is defined as any untoward medical occurrence that, at any dose:

f. Important medical event

- Medical or scientific judgment should be exercised in deciding whether SAE reporting is appropriate in other situations such as important medical events that may not be immediately life-threatening or result in death or hospitalization but may jeopardize the patient or may require medical or surgical intervention to prevent one of the other outcomes listed in the above definition. These events should usually be considered serious.
Examples of such events include invasive or malignant cancers, intensive treatment in an emergency room or at home for allergic bronchospasm, blood dyscrasias, or convulsions that do not result in hospitalization, or development of drug dependency or drug abuse.

Recording and AE and/or SAE

AE and SAE Recording

- When an AE/SAE occurs, it is the responsibility of the Investigator to review all documentation (e.g., hospital progress notes, laboratory reports, and diagnostics reports) related to the event.
- The Investigator will then record all relevant AE/SAE information in the eCRF.
- It is **not** acceptable for the Investigator to send photocopies of the patient's medical records in lieu of completion of the AE/SAE CRF page.
- There may be instances when copies of medical records for certain cases are requested. In this case, all patient identifiers, with the exception of the patient number, will be redacted on the copies of the medical records before submission.
- The Investigator will attempt to establish a diagnosis of the event based on signs, symptoms, and/or other clinical information. Whenever possible, the diagnosis (not the individual signs/symptoms) will be documented as the AE/SAE.

Assessment of Intensity

Intensity of all AEs including clinically significant treatment-emergent laboratory abnormalities, injection site reactions and potential systemic reactions will be graded according to the National Cancer Institute Common Terminology Criteria for Adverse Events (CTCAE), Version 5.0. The CTCAE grade refers to the severity of the AE and ranges from Grade 1 (mild AE), Grade 2 (moderate AE), Grade 3 (severe AE), and Grade 4 (life-threatening or disabling AE) to Grade 5 (death related to AE).

Adverse events not listed by the CTCAE will be graded as follows:

- Mild: An event that is easily tolerated by the patient, causing minimal discomfort and not interfering with everyday activities.
- Moderate: An event that causes sufficiently discomfort and interferes with normal everyday activities.
- Severe: An event that prevents normal everyday activities. An AE that is assessed as severe should not be confused with a SAE. Severe is a category utilized for rating the intensity of an event; and both AEs and SAEs can be assessed as severe.
- An event is defined as 'serious' when it meets at least 1 of the predefined outcomes as described in the definition of an SAE, NOT when it is rated as severe.

Assessment of Causality

- The Investigator is obligated to assess the relationship between trial treatment and each occurrence of each AE/SAE.
- A "reasonable possibility" of a relationship conveys that there are facts, evidence, and/or arguments to suggest a causal relationship, rather than a relationship cannot be ruled out.
- The Investigator will use clinical judgment to determine the relationship.
- Alternative causes, such as underlying disease(s), concomitant therapy, and other risk factors, as well as the temporal relationship of the event to trial treatment administration will be considered and investigated.
- The Investigator will also consult the Investigator's Brochure (IB) and/or Product Information, for marketed products, in his/her assessment.

- For each AE/SAE, the Investigator **must** document in the medical notes that he/she has reviewed the AE/SAE and has provided an assessment of causality.
- There may be situations in which an SAE has occurred and the Investigator has minimal information to include in the initial report. However, **it is very important that the Investigator always make an assessment of causality for every event before the initial transmission of the SAE data.**
- The Investigator may change his/her opinion of causality in light of follow-up information and send a SAE follow-up report with the updated causality assessment.
- The causality assessment is one of the criteria used when determining regulatory reporting requirements.

A medically qualified Investigator must assess the relationship of any AE (including SAEs) to the use of the trial medication, as related or not related, based on clinical judgment and using all available information, and may include consideration of the following factors:

- Possible alternative causes of the AE, including the disease under treatment, pre-existing conditions, concomitant use of other drugs, and presence of environmental or genetic factors.
- The temporal association between trial medication exposure and onset of the AE.
- Whether the manifestations of the AE are consistent with known actions or toxicity of the trial medication.
- The AE resolved or improved with decreasing the dose or stopping use of the trial medication (dechallenge). Judgment should be used if multiple products are discontinued at the same time.

The causal relationship between the trial medication and the AE will be assessed using one of the following categories:

- **Not Related:** Factors consistent with an assessment of Not Related include:
 - Temporal relationship is lacking (e.g., the event did not occur within a reasonable time frame following administration of the trial medication); or
 - Other causative factors more likely explain the event (e.g., a pre-existing condition, other concomitant treatments).
- **Related:** Factors consistent with an assessment of Related include:
 - There is a "reasonable possibility" of a relationship; i.e., there are facts, evidence, and/or arguments to suggest a causal relationship (not just that "a relationship cannot be ruled out");
 - There is a positive temporal relationship (e.g., the event occurred within a reasonable time frame following administration of trial medication);

Assessment of Causality

- The AE is more likely explained by the investigational product than by another cause (i.e., the AE shows a pattern consistent with previous knowledge of the investigational product or the class of the trial medication).

Follow-up of AEs and SAEs

- The Investigator is obligated to perform or arrange for the conduct of supplemental measurements and/or evaluations as medically indicated or as requested to elucidate the nature and/or causality of the AE or SAE as fully as possible. This may include additional laboratory tests or investigations, histopathological examinations, or consultation with other health care professionals.
- If a patient dies during participation in the trial or during a recognized follow-up period, the Investigator will provide a copy of any post-mortem findings including histopathology.
- New or updated information will be recorded in the originally completed CRF.
- The Investigator will submit any updated SAE data to the Sponsor within 24 hours without undue delay but no later than within 24 hours of receipt of the information.

Reporting of SAEs

SAE Reporting via an Electronic Data Collection Tool

- The primary mechanism for reporting an SAE will be the electronic data collection tool.
- If the electronic system is unavailable for more than 24 hours, then the site will use the paper SAE data collection tool (see next section).
- The site will enter the SAE data into the electronic system as soon as it becomes available.
- After the trial is completed at a given site, the electronic data collection tool will be taken off-line to prevent the entry of new data or changes to existing data.
- If a site receives a report of a new SAE from a trial patient or receives updated data on a previously reported SAE after the electronic data collection tool has been taken off-line, then the site can report this information on a paper SAE form (see next section) or by telephone.

SAE Reporting via Paper CRF

- Facsimile transmission of the SAE paper CRF is the preferred method to transmit this information
- In rare circumstances and in the absence of facsimile equipment, notification by telephone is acceptable with a copy of the SAE data collection tool sent by overnight mail or courier service.
- Initial notification via telephone does not replace the need for the Investigator to complete and sign the SAE CRF pages within the designated reporting time frames.
- Contacts for SAE reporting will be provided to sites.

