8.9.11.1. Time Period and Frequency for Collecting AE and SAE Information

All AEs, including SAEs, will be collected from the time informed consent is signed until the EOS visit at the time points designated in the SoA ([Table 1](#) and [Table 2](#)). AEs reported after dosing on Day 1 will be considered TEAEs.

Medical occurrences that begin before the start of trial treatment but after obtaining informed consent will be recorded on the Medical History/Current Medical Conditions section of the eCRF, not in the AE section.

All SAEs will be recorded and reported to the Sponsor or designee within 24 hours without undue delay but no later than within 24 hours, as indicated in [Appendix 5](#). The Investigator will submit any updated SAE data to the Sponsor without undue delay but no later than within 24 hours of it being available.

Investigators are not obligated to actively seek AE or SAE information from former trial patients. However, if the Investigator learns of any SAE, including a death, at any time after a patient has been discharged from the trial, and he/she considers the event to be reasonably related to the trial treatment or trial participation, the Investigator must promptly notify the Sponsor.

The method of recording, evaluating, and assessing causality of AEs and SAEs and the procedures for completing and transmitting SAE reports are provided in [Appendix 5](#).

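### Appendix 5's only outage rule moves SAE reports to paper after more than 24 hours, so a site that follows it literally can miss the 24-hour SAE deadline

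*Protocol*

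**What the plan says.** Section 8.9.11.1 of the protocol sets the limit for a first report: "All SAEs will be recorded and reported to the Sponsor or designee within 24 hours without undue delay but no later than within 24 hours". It points to Appendix 5 for how this is done, and names no event that starts the clock. For new information on a known SAE it says: "The Investigator will submit any updated SAE data to the Sponsor without undue delay but no later than within 24 hours of it being available". Appendix 5 repeats the 24-hour limit for updates, counted from receipt. It does not restate the limit for first reports.

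Under Reporting of SAEs, Appendix 5 gives the routes:

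- The normal route: "The primary mechanism for reporting an SAE will be the electronic data collection tool".
- An outage during the trial: "If the electronic system is unavailable for more than 24 hours, then the site will use the paper SAE data collection tool". The data are then entered electronically once the system is back.
- New or updated SAEs after the tool has been closed at a site that has finished the trial: "after the electronic data collection tool has been taken off-line, then the site can report this information on a paper SAE form", or by telephone.
- Within the paper route, fax is preferred. Telephone is accepted in rare cases where there is no fax, with the form following by overnight mail or courier, and a call "does not replace the need for the Investigator to complete and sign the SAE CRF pages within the designated reporting time frames".

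**The concern.** The deadline and the back-up trigger are both 24 hours long, but they run from different starting points. The deadline runs from the SAE. The trigger runs from the start of the outage. If the SAE came first, its deadline passes before the outage rule calls for paper. If the outage ends within 24 hours, the trigger is never met, yet the deadline may already have passed while the site waited.

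Section 8.9.11.1 sends the site to Appendix 5, so a site looking for instructions during an outage will find this rule and no other. What is at stake is the timeliness of safety reports. Section 8.9.11.4 treats prompt notification as essential to regulatory and ethical duties. The sponsor's reports of suspected unexpected serious reactions, and its lifting of the blind for an unexpected treatment-related SAE (Section 7.2.3), both start from the site's report. The trial plans about 80 centers and enrolls children from age 6.

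**Working it through.** The protocol gives no figure to reproduce. The check is one of timing.

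**Inputs**

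- Deadline: 24 hours (Section 8.9.11.1).
- Paper trigger: electronic system unavailable for more than 24 hours (Appendix 5).
- Assumption: the 24-hour clock starts when the site becomes aware of the SAE.
- Assumption: the site does exactly what the outage rule says. It waits for the system to return or for the trigger to be met, whichever comes first.

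**Outage longer than 24 hours.** Count hours from the start of the outage. Let *a* be the hour at which the site learns of the SAE, negative if before the outage.

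- Deadline = *a* + 24.
- Paper is called for after hour 24.
- Time left at that moment = (*a* + 24) − 24 = *a*.

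The report is therefore late whenever *a* is zero or negative, by more than the number of hours the SAE had already been pending.

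| Site learns of the SAE | Deadline (outage hour) | Paper called for | Result |
|---|---|---|---|
| 12 h before outage | 12 | after hour 24 | more than 12 h late |
| 6 h before | 18 | after hour 24 | more than 6 h late |
| at the start | 24 | after hour 24 | just missed |
| 1 h into outage | 25 | after hour 24 | about 1 h left |
| 6 h into outage | 30 | after hour 24 | about 6 h left |
| 12 h into outage | 36 | after hour 24 | about 12 h left |

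**Outage of *D* hours, with *D* at most 24.** The paper trigger is never met, so the site reports when the system returns, at outage hour *D*. The report is late if *D* > *a* + 24.

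- Aware 12 h before (*a* = −12): late in any outage longer than 12 h.
- Aware 6 h before (*a* = −6): late in any outage longer than 18 h.
- Aware during the outage (*a* > 0): the deadline falls after hour 24, so the report can be on time.

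**Does other text supply an earlier written route?** The second paper or telephone rule in Appendix 5 applies only after the tool has been closed at a site that has completed the trial. The telephone option sits inside the paper route, and a call does not stand in for the signed pages. The opening of Section 8 asks that immediate safety concerns be discussed with the sponsor at once, and Section 8.9.11.4 stresses promptness, but neither provides a written SAE report. Section 8.9.11.3 and the COVID-19 guidance in Appendix 6 give no outage fallback.

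**The case against.** The best reply is that the two rules do not exclude each other. A reader might infer that they cannot both be followed, and the text does not support that. Appendix 5 says when a site will go to paper; it does not bar paper before then. It calls the electronic tool the primary route, not the sole one. Section 8.9.11.1 binds throughout, so a site that sends paper early breaks neither rule. This stands, and it limits the charge. The fault is an instruction that leads to a late report when taken literally, not an impossible pair of duties. It does not remove the fault, because a site has to go beyond the only stated outage procedure to meet the deadline.

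Second, Section 8 calls for immediate discussion of safety concerns, and Appendix 5 promises contacts for SAE reporting. The sponsor may therefore hear of an urgent event during an outage. This also stands, but a conversation is not the written report.

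Third, a site that reports without undue delay rarely has an SAE pending for long. If sites report within 4 hours of awareness (an assumption), a pending SAE is late only in an outage longer than 24 − 4 = 20 hours, and then by little. This shows that the size depends on site habits and outage lengths, which the documents do not give. One might be tempted to turn outage length into a percentage of late reports, but that would need an assumed spread of awareness times for which there is no support.

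Fourth, a reader might extend the harm to the Data Safety Monitoring Board. It meets at intervals of about 3 months (Section 9), so a delay of hours has a negligible effect there. Emergency unblinding is also untouched: Section 7.2.3 leaves it to the investigator through the randomization system.

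**Conclusion.** The concern holds in a limited form. The one outage rule in Appendix 5 does not fit the 24-hour deadline that Section 8.9.11.1 says Appendix 5 implements. Followed literally, it makes a report late in two cases: an SAE known and unreported when an outage of more than 24 hours begins, and an SAE pending at the start of a shorter outage that outlasts the time left on its clock. In the first case the delay exceeds the hours the SAE was already pending. The same reasoning applies to SAE updates, which carry their own 24-hour limit.

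The conclusion rests on a clock that starts at site awareness and on a site that uses no route beyond the stated one. The documents give no outage frequency, so the expected number of late reports cannot be stated. The point concerns safety-reporting procedure only and changes no endpoint, analysis set or efficacy estimate. It is worth correcting because a written rule gives the wrong result and one sentence repairs it.

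**What to change.** Reconcile Section 8.9.11.1 with the electronic and paper reporting parts of Appendix 5. Replace the outage trigger with: *If the electronic system is unavailable and the SAE could not otherwise be reported within 24 hours of site awareness, the site will send the paper SAE form within that 24-hour limit and enter the data electronically when the system is available.* State in Section 8.9.11.1 that the clock starts at site awareness, and let the time frames mentioned in the paper section refer to that same limit.

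This wording does not require paper for a brief interruption when ample time remains. The cost is occasional double entry and inclusion in a protocol amendment, which under Appendix 7 needs ethics approval before it takes effect, across about 80 planned centers. It can go into the next amendment, with a reminder to sites.
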